10.1 Adverse Event Definitions

Adverse Event (AE): any untoward medical occurrence in a patient or clinical study subject.

Serious Adverse Event (SAE): any untoward and unexpected medical occurrence or effect that:

- Results in death
- Is life-threatening – refers to an event in which the subject was at risk of death at the time of the even; it does not refer to an event which hypothetically might have caused death if more severe.
- Requires hospitalisation (>24 hrs), or prolongation of existing inpatient hospitalisation
- Results in persistent or significant disability or incapacity
- Is a congenital anomaly or birth defect

Medical judgement should be exercised in deciding whether an AE is serious in other situations. Important AEs that are not immediately life-threatening or do not result in death or hospitalisation but may jeopardise the subject or may require intervention to prevent one of the other outcomes listed in the definitions above, should also be considered serious.

Any Adverse Events that are related to atrial arrhythmia will be reported as endpoints rather than Adverse Events. Serious Adverse Events that are related to atrial arrhythmia must be reported as SAEs.

Any planned hospitalisations such a for a redo ablation procedure prior to entry into the Discharge protocol or planned surgery will not be reported as Serious Adverse Events as these are expected.

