10.2 Expected Serious Adverse Events

- Symptoms of atrial fibrillation/tachycardia
- Pericardial Effusion
- Vascular Bleeding
- Phrenic Nerve Palsy
- PV stenosis
- Shortness of Breath more than 1 week from the procedure
- Chest pain more than 1 week from the procedure

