10.5 Reporting Procedures

All adverse events should be reported via the eCRF within 24 hours of awareness of the event. All adverse events occurring between randomisation and the patient's last study follow-up visit will be reported. All adverse events will be followed up until resolution or until the end of trial..

Adverse events for any patients who withdraw from the study prematurely should be collected and followed up through at least the time of discontinuation.

Depending on the nature of the event, the reporting procedures should be followed. All questions concerning adverse event reporting should be directed to the Chief Investigator in the first instance.

Non-Serious AEs

All such events, whether expected or not, should be recorded on the eCRF.

Serious AEs

An SAE form should be completed via the eCRF within 24 hours of awareness of the event. The Chief Investigator or designee will review each SAE via the eCRF,

Please refer to section 7.1 Adverse Event Definitions for further clarification on definitions of AEs and SAEs and how to report in relation to study endpoints.

Related and Unexpected SAEs

All SAEs should be reported to the NRES Committee London - Brent (United Kingdom) where in the opinion of the Chief Investigator, the event was:

- 'related', ie resulted from the administration of any of the research procedures; and
- 'unexpected', ie an event that is not listed in the protocol as an expected occurrence

Local Investigators should report any SAEs as required by the Sponsor, Research & Development office and other appropriate authorities/committees.

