14.2 Data & Safety Monitoring Board (DSMB)

An independent Data & Safety Monitoring Board (DSMB) will be convened and meet to provide independent advice on study conduct and safety issues. The DSMB will meet at the start of the trial and as required thereafter based on planned interim analyses. Meetings will be held approximately annually or as required throughout the duration of the trial. Safety data will be studied after 75 and 150 patients have received treatment, or one year after the first patient is randomised, whichever occurs sooner. Meetings will also be held as necessary should any urgent issues occur. The DSMB will develop a charter which describes the framework within which it will operate.

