***Table Note: To include for all Anti-Arrhythmics and Beta-Blockers**

Table 6.5: Review of Intervention (Anti-Arrhythmic Arm)

Variable	Statistics	Week 4 Review	Week 8 Review
Number of Subjects	N		
Was treatment changed at review? (%)	No Increased Decreased Change of Agent		

SAFETY AND EFFICACY – ADVERSE EVENTS

Table 7.1: Summary of Adverse Events by Treatment and Severity

		Events				Patients			
		AVATAR-AF Ablation	Anti-arrhythmic therapy	Conventional AF Ablation	Total	AVATAR-AF Ablation	Anti-arrhythmic therapy	Conventional AF Ablation	Total
Reason for SAE	Number of Adverse events	Mild							
	Moderate								
	Severe								
	Number of SAEs	Missing							
	Death								
	Hospitalisation required								
	Life threatening								
	Other medical important events								
	Total								

Table 7.2: Number of Adverse Events by Treatment and causality relationship

Treatment	Subjects with AEs*						
	No Relationship	Unlikely	Possible	Probable	Definitely	Not Yet Defined	Total
AVATAR-AF protocol ablation							
Anti-arrhythmic therapy							
Conventional AF ablation							
All subjects							

		All AEs						
Treatment		No Relationship	Unlikely	Possible	Probable	Definitely	Not Yet Defined	Total
AVATAR-AF protocol ablation								
Anti-arrhythmic therapy								
Conventional AF ablation								
All subjects								

*Table Note: Where subjects have more than one AE the highest relationship has been used.

Table 7.3: Listing of Serious Adverse Events

Treatment	Subject	AE Diagnosis	Details			Relation to Treatment	Surgery Required?

Table 7.3: Listing of Serious Adverse Events (Continued)

Treatment	Subject	Start Date	Recovery Date	Expected-ness	Event Frequency	Comments	

Table 7.4: Number of Serious Adverse Events by Treatment and causality relationship

		Subjects with SAEs*						
Treatment		No Relationship	Unlikely	Possible	Probable	Definitely	Not Yet Defined	Total
AVATAR-AF protocol ablation								
Anti-arrhythmic therapy								
Conventional AF ablation								
All subjects								

Treatment	All SAEs						
	No Relationship	Unlikely	Possible	Probable	Definitely	Not Yet Defined	Total
AVATAR-AF protocol ablation							
Anti-arrhythmic therapy							
Conventional AF ablation							
All subjects							

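### Protocol 10.1 makes being unexpected part of the SAE definition, which contradicts the protocol's own list of expected SAEs, its reporting steps and SAP Table 7.3

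*Protocol*

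**What the plan says.** **Definition (Protocol 10.1).** An SAE is "any untoward and unexpected medical occurrence or effect that" leads to death, threatens life, needs or prolongs hospitalisation, causes disability, or is a congenital anomaly. The same section exempts planned admissions, such as a scheduled redo ablation, from SAE reporting and gives their being expected as the reason. It also states: "Serious Adverse Events that are related to atrial arrhythmia must be reported as SAEs".

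**List (Protocol 10.2).** Under the title "Expected Serious Adverse Events" there are seven entries: symptoms of atrial fibrillation or tachycardia, pericardial effusion, vascular bleeding, phrenic nerve palsy, PV stenosis, and breathlessness or chest pain arising more than a week after the procedure.

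**Reporting (Protocol 10.5).** For SAEs, "An SAE form should be completed via the eCRF within 24 hours of awareness of the event", and the Chief Investigator or a designee reviews each one. A separate paragraph covers the ethics committee: "All SAEs should be reported to the NRES Committee London - Brent (United Kingdom) where in the opinion of the Chief Investigator, the event was" both related and unexpected. Unexpected is explained there as "an event that is not listed in the protocol as an expected occurrence".

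**Tables (SAP 8.7).** Table 7.3, the SAE listing, has a column headed "Expected-ness". Tables 7.1 and 7.4 count SAEs by treatment arm.

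**The concern.** Seriousness and expectedness are different properties. Seriousness decides whether an SAE form is filed. Expectedness decides who else must be told. Section 10.1 merges the two, while the rest of the plan keeps them apart.

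The events at stake are the serious procedural complications named in 10.2. They matter here because the AVATAR arm is a same-day-discharge procedure. If a site follows the definition as written, such an event may get no SAE form, no SAE review and no place in the SAE tables. If another of the 13 sites follows the 10.2 title instead, the SAE counts are not comparable between sites.

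**Working it through.** No arithmetic applies, because no rate, sample size or test is involved. The check sets the sections side by side.

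1. **The literal chain.** By 10.1 an SAE must be unexpected. By 10.5 an event is unexpected if the protocol does not list it as expected. By 10.2 pericardial effusion, vascular bleeding, phrenic nerve palsy and PV stenosis are listed. So a serious event of these four kinds fails the 10.1 definition. One step is an inference: 10.1 does not itself define unexpected, and the meaning is borrowed from 10.5.

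2. **Against the 10.2 title.** The list is of SAEs that are expected. Under 10.1 that class is empty.

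3. **Against the 10.5 sequence.** The SAE form carries no expectedness condition. Unexpectedness appears only at the next step, to select reports for the ethics committee. If every SAE were unexpected by definition, that selection would be redundant.

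4. **Against 10.1 itself.** Serious arrhythmia-related events must be reported as SAEs, yet arrhythmia symptoms are on the expected list. One section thus both excludes and requires the same kind of event.

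5. **Against SAP Table 7.3.** An expectedness column is needed only if SAEs can be of either kind.

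6. **Text that encourages the literal reading.** The planned-admission exemption uses expectedness as a reason not to report. A site looking for clarification is sent by 10.5 to section 7.1, which is the Discharge Protocol; the definitions are in 10.1.

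7. **What changes under the literal reading.** For a listed complication the SAE form, the Chief Investigator's SAE review and the entries in SAP Tables 7.1 (SAE rows), 7.3 and 7.4 would be missing. Reporting to the ethics committee would not change, because a listed event is filtered out there either way.

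8. **What is still captured.** Protocol 10.5 requires all adverse events on the eCRF within 24 hours, and SAP Table 7.1 counts them by severity. Protocol 8.2 makes complications secondary endpoint 2, 8.4 has them adjudicated, SAP 7.2 names all four kinds, and SAP Tables 5.4 to 5.6 list and compare them.

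9. **Which events are affected.** Of the seven entries in 10.2, six (7 − 1) are procedural complications or symptoms timed from the procedure. The other is arrhythmia symptoms. No drug reaction is listed.

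**The case against.** The strongest reply is that the intention is clear. The 10.2 title, the 10.5 sequence, the arrhythmia sentence and the SAP column all point to one meaning, and 10.1 adds a medical-judgement route to seriousness that does not mention expectedness. A sensible investigator would file the form. The planned-admission sentence concerns scheduled care, not complications. All of this stands as evidence of intent. It does not remove the fault, because the operative definition still says something else.

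Four stronger readings are tempting, and the documents do not support them.

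- **That the main ablation complications can never be SAEs.** The list itself calls them SAEs. It is also incomplete: atrio-oesophageal fistula, mentioned in Protocol 1.1, and stroke are not on it, so they would be SAEs even under the literal rule.
- **That safety data would be lost or hidden from the DSMB.** Item 8 of the working shows two other routes of capture. Protocol 14.2 says "Safety data will be studied after 75 and 150 patients have received treatment", which is not limited to SAE forms, and SAP 8.6 puts safety endpoints in the interim reports.
- **That the SAE comparison is biased in favour of ablation.** Dropping procedural events would lower the ablation counts. But arrhythmia symptoms are also listed, and Protocol 11.1 assumes arrhythmia-related hospital episodes are most frequent on drugs (0.63, against 0.40 for AVATAR and 0.20 for conventional ablation). Dropping those would pull the other way. If the arrhythmia sentence in 10.1 keeps them in, the protocol is counting a listed event as an SAE, which weakens the literal reading.
- **That up to 100% of listed serious events would go unreported as SAEs.** This only restates the definition for a hypothetical site. It is not an estimate.

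**Conclusion.** The contradiction is real, and the definition is wrong as written: followed to the letter, it would leave serious procedural events unclassified as SAEs. The consequence is limited to SAE misclassification and uneven reporting between sites, mostly for procedural events, with the loss of SAE-level review that follows. It does not extend to loss of the underlying data.

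The size cannot be given. The documents contain no complication rates and no indication of how any site reads 10.1, so neither the number of affected events nor the net direction of a between-arm difference can be derived. The conclusion assumes that the 10.5 meaning of unexpected carries back to 10.1. If it does not, the word is undefined in 10.1, and the conflict with the 10.2 title and SAP Table 7.3 remains.

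**What to change.** - Delete the words *and unexpected* from the SAE definition in Protocol 10.1.
- Keep expectedness in two places only: the 10.5 filter for the ethics committee and the attribute in SAP Table 7.3.
- Rest the exemption for planned admissions on their being planned, not on their being expected.
- Correct the cross-reference in 10.5 from section 7.1 to 10.1.
- If events have already been collected, check adverse events in the 10.2 categories against the seriousness criteria before the SAE tables are produced.

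The cost is a wording change, a note to sites and a few more SAE forms. The listed events would still not go to the ethics committee, so that workload should not change.

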10.2 Expected Serious Adverse Events

- Symptoms of atrial fibrillation/tachycardia
- Pericardial Effusion
- Vascular Bleeding
- Phrenic Nerve Palsy
- PV stenosis
- Shortness of Breath more than 1 week from the procedure
- Chest pain more than 1 week from the procedure

10.3 Adverse Event Intensity or Severity

The intensity or severity of each adverse event should be classified by the investigator according to the following guidelines:

Intensity	Description
Mild	Any event that results in minimal transient impairment of a body function and does not threaten damage to a body structure, and/or does not require intervention other than monitoring.

Moderate	Any event which results in moderate transient impairment of a body function or damage to a body structure, or which requires intervention.
Severe	Any event which is life threatening, results or could result in significant permanent impairment of a body function or damage to a body structure, requires significant and timely intervention to prevent permanent impairment of a body function or damage to a body structure, or which is intolerable or places the subject at immediate risk of harm.

10.4 Adverse Event Causality

The assignment of the causality should be made by the investigator responsible for the care of the participant using the definitions in the table below.

Relationship	Description
Unrelated	There is no evidence of a causal relationship with the anti-arrhythmic therapy or ablative therapy.
Unlikely	There is little evidence to suggest a causal relationship with the anti-arrhythmic or ablative therapy (e.g the event did not occur within a reasonable time after study treatment). There is another reasonable explanation for the event (e.g the participant's clinical condition, other concomitant treatments).
Possible	There is some evidence to suggest a causal relationship with the anti-arrhythmic or ablative therapy (because the event occurs within a reasonable time after the study therapy). However, the influence of other factors may have contributed to the event (e.g the participant's clinical condition, other concomitant treatments).
Probable	There is evidence to suggest a causal relationship with the anti-arrhythmic or ablative therapy and the influence of other factors is unlikely.
Definitely	There is clear evidence to suggest a causal relationship with the anti-arrhythmic or ablative therapy and other contributing factors can be ruled out.
Not Assessable	There is insufficient or incomplete evidence to make a clinical judgement of the causal relationship.

10.5 Reporting Procedures

All adverse events should be reported via the eCRF within 24 hours of awareness of the event. All adverse events occurring between randomisation and the patient's last study follow-up visit will be reported. All adverse events will be followed up until resolution or until the end of trial..

Adverse events for any patients who withdraw from the study prematurely should be collected and followed up through at least the time of discontinuation.

Depending on the nature of the event, the reporting procedures should be followed. All questions concerning adverse event reporting should be directed to the Chief Investigator in the first instance.

Non-Serious AEs

All such events, whether expected or not, should be recorded on the eCRF.

Serious AEs

An SAE form should be completed via the eCRF within 24 hours of awareness of the event. The Chief Investigator or designee will review each SAE via the eCRF,

Please refer to section 7.1 Adverse Event Definitions for further clarification on definitions of AEs and SAEs and how to report in relation to study endpoints.

Related and Unexpected SAEs

All SAEs should be reported to the NRES Committee London - Brent (United Kingdom) where in the opinion of the Chief Investigator, the event was:

- 'related', ie resulted from the administration of any of the research procedures; and
- 'unexpected', ie an event that is not listed in the protocol as an expected occurrence

Local Investigators should report any SAEs as required by the Sponsor, Research & Development office and other appropriate authorities/committees.

11 STATISTICAL ANALYSIS

11.1 Sample Size Calculation

In this time-to-event study of hospital episodes, required sample numbers have been estimated using the log-rank test under the Freedman method based on the occurrence of first event during the 12-month follow-up period. The null hypothesis is that there is no difference in the distributions. Adopting a conservative approach, an initial two-sided alpha of 0.05 is chosen, given the need to allow for the inherent multiple testing between the three arms of the study, the conservative Bonferroni correction is applied and the alpha value used in the power calculations is reduced to 0.025.

Estimating the proportion experiencing a hospital episode in the follow-up period in the anti-arrhythmic arm as 0.63 and the corresponding proportion in the AVATAR ablation arm as 0.40, assuming the occurrence of 103 events, with 100 evaluable patients in each of the two treatment arms yields a power of 0.8. A similar power is obtained for the comparison of the AVATAR ablation arm (0.40) and the conventional AF ablation arm (0.20).

A sensitivity analysis indicates that these sample size estimates are reasonable. It is anticipated that the loss to follow-up will be small, approximately 7%. Consequently, 321 patients will be randomised in a 1:1:1 manner to a treatment strategy of either AVATAR-protocol ablation, anti-arrhythmic therapy or conventional AF ablation and followed-up for 1 year.

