11.2 Data Analysis

Primary outcome: Failure is counted when a patient experiences any hospital episode related to treatment for atrial arrhythmia. Patients are censored from their treatment group when they switch to a treatment other than that to which they were originally assigned or when they leave their treatment group without having experienced a hospital episode.

Data will be analyzed using the intention-to-treat principle and a p value of 0.05 or less will be considered significant. Primary outcome will be analysed using Kaplan-Meier statistics and differences will be tested using log-rank test and proportional hazards models. Other outcomes will be compared using t-test for continuous and Chi-square test or Fisher exact test for categorical variables and the appropriate generalized linear model will be used.

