8.2. Primary Endpoint Analysis

Failure is counted when a patient experiences any hospital episode related to treatment for atrial arrhythmia. Time to failure will be taken as the time from 1st Intervention to the time of event.

Data will be analysed using the intention-to-treat principle and a p-value of 0.025 or less will be considered significant. Primary outcome will be analysed using Kaplan-Meier statistics and differences between treatment arms will be assessed using log-rank testing and proportional hazards models. Models containing one or more of the following covariates may also be assessed if deemed necessary; site, weight, hypertension, number of anti-arrhythmic taken by patient prior to 1st intervention.

Primary endpoint analysis will be carried out between AVATAR-AF Ablation and the Anti-Arrhythmic drug treatment arm in order to investigate the primary objective. The secondary objective will be assessed by testing AVATAR-AF Ablation against the Conventional Ablation arm.

An additional per-protocol analysis will be carried out in conjunction with the above.

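### Two comparisons are tested by plain Bonferroni; Holm's procedure would hold the same family-wise 0.05 with more power at the design rates, and would replace two conflicting thresholds

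*Protocol*

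**What the plan says.** Protocol 11.1 and SAP 5.5 start from 0.05 ("an initial two-sided alpha of 0.05 is chosen") and divide it because there are several arms: "the conservative Bonferroni correction is applied", giving 0.025 for each comparison. SAP 8.2 carries this into the analysis of the primary endpoint: "a p-value of 0.025 or less will be considered significant". It names two comparisons. AVATAR against anti-arrhythmic drugs serves the primary objective, and AVATAR against conventional ablation serves the secondary objective. Protocol 11.2 gives a different threshold for the analysis, with no mention of a correction: "a p value of 0.05 or less will be considered significant". Neither document describes a step-down or hierarchical rule. The Cox tables in SAP 8.7 (4.3, 5.3, 5.6 and 5.9) plan 95% confidence intervals.

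**The concern.** With two comparisons and a family-wise 0.05, plain Bonferroni keeps the second test at 0.025 even after the first null hypothesis has been rejected. Holm's procedure tests the smaller p-value at 0.025 and, if that is significant, the larger at 0.05. The plan protects the family-wise error but gives up some power that the same protection would allow, and it gives no reason for doing so beyond wishing to be conservative.

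The two documents also disagree. A primary-endpoint p-value between 0.025 and 0.05 is significant under Protocol 11.2 and not under SAP 8.2. If Protocol 11.2 were followed for both comparisons, the family-wise error would be bounded only by 2 × 0.05 = 0.10. This text has to be amended in any case, so the choice of procedure can be settled at the same time.

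**Working it through.** **Inputs (Protocol 11.1, repeated in SAP 5.5).**
- Method: "estimated using the log-rank test under the Freedman method".
- Primary comparison: event proportions 0.63 (drugs) and 0.40 (AVATAR). Events, numbers and power: "assuming the occurrence of 103 events, with 100 evaluable patients in each of the two treatment arms yields a power of 0.8".
- Second comparison: 0.40 (AVATAR) against 0.20 (conventional), with power described as similar. With 100 per arm this implies 40 + 20 = 60 events.
- Assumptions of this check: proportional hazards, and a correlation of −0.5 between the two statistics when each is signed in the direction of its planned effect. The arms are equal in size and AVATAR is shared, as the better arm in one test and the worse arm in the other. A three-arm log-rank simulation gave a correlation of 0.49 in size, in agreement.

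**Step 1. Hazard ratios and drifts.** HR = ln(1 − p_low) / ln(1 − p_high); Freedman drift = √d × (1 − HR)/(1 + HR).
- AVATAR v drugs: HR = ln 0.60 / ln 0.37 = 0.514; drift = √103 × 0.486/1.514 = 3.26.
- AVATAR v conventional: HR = ln 0.80 / ln 0.60 = 0.437; drift = √60 × 0.563/1.437 = 3.04.

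**Step 2. The plan's own power.** Power = Φ(drift − z), with z = 2.241 for two-sided 0.025.
- AVATAR v drugs: Φ(3.26 − 2.241) = 0.846. The stated 0.80 is not reproduced at 0.025. At 0.017, the alpha that the SAP revision history says was replaced, the result is 0.809.
- AVATAR v conventional: Φ(3.04 − 2.241) = 0.787, consistent with similar to 0.80.

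**Step 3. Error control under Holm.** If both nulls are true, a false rejection requires at least one p-value at or below 0.025, which has probability at most 2 × 0.025 = 0.05 under any dependence. If one null is true, rejecting it requires its own p-value to be at or below 0.05. Every Bonferroni rejection is also a Holm rejection. With both nulls true and correlation −0.5, the family-wise error is 4.6% under either procedure.

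**Step 4. Power at the design rates** (bivariate normal, drifts 3.26 and 3.04, correlation −0.5).

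| | Bonferroni | Holm |
|---|---|---|
| AVATAR v drugs | 0.846 | 0.900 |
| AVATAR v conventional | 0.787 | 0.856 |
| Both significant | 0.639 | 0.762 |
| At least one significant | 0.994 | 0.994 |

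The gains are 5.4 and 6.9 points. Schoenfeld drifts give 4.8 and 5.9; log-rank simulation (20,000 trials, exponential times) gives 4.8 and 6.4; starting both comparisons from the stated 0.80 gives 6.5 each.

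**Step 5. Dependence on the other comparison.** Hold AVATAR v drugs at the design rates and move the conventional-arm rate towards AVATAR's 0.40.

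| Conventional-arm rate | Primary comparison, Bonferroni to Holm | Gain (points) |
|---|---|---|
| 0.20 | 0.846 to 0.900 | 5.4 |
| 0.30 | 0.846 to 0.870 | 2.4 |
| 0.35 | 0.846 to 0.854 | 0.8 |
| 0.40 | 0.846 to 0.848 | 0.2 |

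The second comparison keeps more of its gain, because the primary one is likely to be rejected: at a conventional-arm rate of 0.30 its power goes from 0.23 to 0.30.

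**Step 6. The price.** If AVATAR beats drugs as planned but equals conventional ablation (0.40 v 0.40), the chance of declaring a false difference between the two ablations rises from 2.5% to about 4.3%.

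**The case against.** Bonferroni was chosen openly, is valid and is pre-specified. It lets each objective stand alone. Under Holm at these rates, a primary p-value between 0.025 and 0.05 becomes significant only when the secondary comparison is significant too, which here means that AVATAR did worse than conventional ablation. A sponsor who believes that mapping is unnecessary might not want the primary claim to rest on that. All of this stands, and it is a legitimate reason to keep Bonferroni if the sponsor states it.

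Three stronger readings are tempting, and the documents do not support them.
- A reader might infer that the multiplicity adjustment is wrong. It is not: 0.025 twice controls the family-wise error at 0.05.
- A reader might infer that Holm adds 5 to 7 points to each comparison whatever happens, at no cost. The gain is conditional (step 5), tighter control of each single comparison is given up (step 6), and Holm has no simple matching simultaneous confidence intervals. The last loss is small here, because the SAP tables plan 95% intervals, which do not match the 0.025 threshold either.
- A reader might infer that the trial is underpowered without Holm. Under Bonferroni the recomputed power is 0.846 and 0.787, so the planned 0.80 is essentially met.

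**Conclusion.** The point holds as a missed efficiency together with an inconsistency between the documents. At the design rates, Holm raises power by about 5 points for AVATAR v drugs, by about 6 to 7 points for AVATAR v conventional ablation, and by about 12 points for both (0.64 to 0.76), at the same family-wise 0.05. The chance of winning at least one comparison does not change.

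These figures rest on proportional hazards, 100 evaluable patients per arm, the planned proportions and a correlation of −0.5. The primary gain shrinks to 2.4 points or less once the conventional-arm rate is 0.30 or higher, and almost vanishes if the two ablations perform alike. The conflict between 0.05 in Protocol 11.2 and 0.025 in SAP 8.2 needs resolving whichever procedure is chosen.

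**What to change.** In SAP 8.2 and Protocol 11.2, replace the conflicting 0.025 and 0.05 for the primary endpoint with:

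> The two comparisons are tested by Holm's procedure at family-wise two-sided 0.05: the smaller p-value against 0.025 and, if significant, the larger against 0.05.

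State the confidence level to be reported. The SAP tables now plan 95%; 97.5% intervals would match the first step and be somewhat conservative for the second. Make the change before any comparative analysis. If the sponsor prefers to keep Bonferroni so that each objective stands alone, say so and change Protocol 11.2 to 0.025.

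The sentence covers the primary endpoint only. The threshold for other outcomes (0.05 in Protocol 11.2, 0.025 for the safety variables in SAP 8.4) should be aligned in the same amendment.

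Cost: one sentence in each document and a stated interval level. No patients, visits or data change. The statistical price is the one given in step 6, together with the lack of simple matching simultaneous intervals.
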